
PD Pharmacodynamic

pHLH Primary hemophagocytic lymphohistiocytosis

PLT Platelets

PK Pharmacokinetic

PPD Purified protein derivative

PT Prothrombin time

QOL Quality of life

REB Research ethics boards

ROC Receiver operating characteristic

RSI Reference safety information

SAE Serious adverse event
SAP Statistical analysis plan

sCD25 Soluble CD25 (i.e., soluble IL-2 receptor)

SD Study day

SD(n) Study day number (e.g., Study day 1 = SD1)

sHLH Secondary hemophagocytic lymphohistiocytosis

sJIA Systemic juvenile idiopathic arthritis

SUSAR Suspected unexpected serious adverse reaction

TB Tuberculosis

TEAE treatment-emergent adverse event

TG Triglycerides

TLR9 Toll-like receptor-9
TMF Trial master file

TP-DI Therapeutic protein-drug interactions

US Ultrasound

USA United States of America

Wk Week

Table 1: Schedule of Assessments – Screening and Treatment Period

	Assessments	Screening Visit (up to 2 Weeks	Week 1		Week 2 →	Week 8 Assessment Visit	EOT (3±1 days after last inf.)	UV °
		prior to Visit 1)	Visit 1 / SD0	Visit 2 / SD3	Visit 3 onwards	Visit X ^a	Visit X ^b	
Dexamethasone ^d		Х						
Anti-viral Prophyla	axis ^d	Х						
Informed Consent	nformed Consent/Assent X							
Infusion ^e			Х	х	Х	х		
Patient Information	on f	Х						
	Vital Signs ^g	Х	X (Pre/post-inf.)	X (Pre/post-inf.)	X (Pre/post-inf.)	X (Pre/post-inf.)	Х	
Clinical	Physical Examination h	х	X (Pre-inf.)	X (Pre-inf.)	X (Pre-inf.)	X (Pre-inf.)	Х	
Assessments	QOL - PedsQL ^{™,} Pediatric Quality of Life Inventory [™]	Х			Χ°	х	Х	
	QOL – BASES P						Х	
Procedure	ECG	Х					Х	
	TB i	Х	X (every 4 weeks)					
Search for Infections	Infection search & monitoring	X (at minimum EBV & CMV viral loads)	n case of suspicion of infection or if there is an active infection at screening/baseline to monitor evolution of viral load and positivity for an identified pathogen					
	Atypical mycobacteria, Histoplasma capsulatum, Shigella, Salmonella, Campylobacter, Leishmania	Х	In case of suspicion of infection					
	CBC ^t	х	X (Pre-inf.)	X (Pre-inf.)	X (Pre-inf.)	X (Pre-inf.)	X	
	Coagulation ^t	x	X (Pre-inf.)	X (Pre-inf.)	X (Pre-inf.)	X (Pre-inf.)	Х	
Laboratory	Biochemistry ^t	Х	X (Pre-inf.)	X (Pre-inf.)	X (Pre-inf.)	X (Pre-inf.)	X	
	Pregnancy Test (if applicable)	X					Х	
	Urinalysis ^j		Х				Х	
	Abdominal Ultrasound ^{k,t}	Х		X (every 2 weeks)		Х	Х	

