Imaging	Chest X-ray ^{u,t}	Х	If clinically indicated (e.g. in case of clinical suspicion of pulmonary infection or to follow-up a pre- existing infection at screening/baseline)					
	Brain MRI ^{l,t}	Χı	If clinically inc	dicated (to monitor ev	volution or to confirm o	ccurrence of new CN	S symptoms)	
Histopathology	CSF Analysis (if coagulation allows) ^m	Х	If clinically indicat	If clinically indicated (to monitor evolution of CSF abnormalities or in case of occurrence of new CNS symptoms)				

Assessments	Screening Visit (up to 2 Weeks prior to Visit 1)	Week 1		Week 2 >	Week 8 Assessment Visit	EOT (3±1 days after last inf.)	UV ¢
		Visit 1 / SD0	Visit 2 / SD3	Visit 3 onwards	Visit X ^a	Visit X ^b	
Assessment of clinical response		X (every 2 weeks)			Х	Х	
AE Recording ^s		х	х	Х	Х	Х	Х
IMP Handling (Preparation, Dispensing, Accountability)		Х	х	Х	Х		
PK (Emapalumab Concentration)		X (Pre - post inf.)	X (Pre - post inf.)	X (Pre - post inf.) ⁿ	X (Pre - post inf.)	Х	
PD (CXCL9, CXCL10, sCD25), total IFNγ, and other exploratory biomarkers		X (Pre - inf)	X (Pre-inf.)	X (Pre-inf.) n	X (Pre-inf.)	Х	
Immunogenicity (ADAs)		Х		Χd	Х	х	

Abbreviations: ADAs, anti-drug antibodies; AE, adverse event; ALP, alkaline phosphatase; ALT, alanine transaminase, aPTT, activated partial thromboplastin time; AST, aspartate transaminase; CBC, complete blood count; CMV, cytomegalovirus; CNS, central nervous system; CRP, C-reactive protein; CSF, cerebrospinal fluid; EBV, Epstein-Barr virus; ECG, electrocardiogram; EOT, end of treatment; yGT, gamma glutamyl transferase; HLH, hemophagocytic lymphohistiocytosis; HSCT, hematopoietic stem cell transplantation; ICF, informed consent form; IGRA, interferon-gamma release assays; IFNy, interferon gamma; IMP, investigational medicinal product; inf, infusion; INR, International normalized ratio; IRR, infusion related reaction; LDH, lactate dehydrogenase; LUC, large unstained cells; MRI, magnetic resonance imaging; PCR, polymerase chain reaction; PD, pharmacodynamic; PK, pharmacokinetic; PPD, purified protein derivative; PT, prothrombin time; QOL, quality of life; SD, study day; TB, tuberculosis; US, ultrasound

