- ⁸ Vital Signs: include body temperature, heart rate, blood pressure, oxygen saturation. Temperature is to be measured pre-infusion, at the end of the infusion, 1 hour and 2 hours after the end of each infusion. For the first infusion for each patient (SD0), for the first infusion at an increased dose and/or for any infusions in a patient who has experienced an IRR (defined as signs or symptoms with a temporal relationship to the administration of an infusion and assessed as related, occurring typically soon following the start of the infusion, although symptoms may be delayed for up to 24h; they might be limited (skin reaction), or systemic), blood pressure, heart rate and oxygen saturation are to be collected every 15 minutes during and until the end of the infusion, 1 hour and 2 hours after the end of the infusion. After the first infusion in all other cases, blood pressure, heart rate and oxygen saturation can be collected pre-infusion, at 30 minutes after the beginning of the infusion, at the end of the infusion, 1 hour and 2 hours after the end of the infusion
- h Physical Examination includes as a minimum: weight, height/length (at screening only), spleen and liver size (by abdominal palpation), neurological examination
- ⁱ **TB:** search for tuberculosis mycobacteria: at screening: IGRA/PPD and PCR; after screening by PCR.
- ^j Urinalysis: glucose, blood, protein and/or albumin, leukocytes, ketones, pH, gravity
- k Abdominal ultrasound: must include longitudinal measure of spleen. At SDO only if 2 weeks elapsed between the screening visit and SDO.

- ¹ Brain MRI: to be performed in case of CNS disease and/or onset of neurological signs and/or symptoms. Brain CT or cranial ultrasound will be accepted as a replacement of brain MRI.
- m CSF analysis: if lumbar puncture is performed at the site for monitoring/therapy of CNS disease, spare sample (if any) may be analyzed for emapalumab and biomarkers levels
- ⁿ PK & PD samplings: from Visit 3 onwards, every other infusion
- ^o QOL, PedsQL: to be performed post-infusion at Visit 3
- PQOL, BASES: if HSCT is planned
- ^q Immunogenicity (ADAs): only at Week 4, to be collected together with a PK sample
- SAE recording: all AEs are collected after signing of ICF up to Study Completion or until serum levels of emapalumab are no longer detectable (whichever occurs first)

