8 OUTLINE OF STUDY PROCEDURES

Patients will be recruited from specialized study sites, equipped with an intensive care unit and access to a bone marrow transplant unit.

Patients will be in the treating unit the day before the first administration of emapalumab (Study Day minus one, SD-1).

For a detailed description of the schedule of visits and assessments, refer to the Schedule of Assessment Table 1 (Screening and Treatment Period) and Table 2 (Follow-up Period).

Informed consent form must be signed by the patient or his/her legally authorized representative prior to any study-related procedures, with the assent of patients who are deemed suitable to provide it.

During the emapalumab treatment period, visits for infusion and efficacy/safety assessments will occur on SD0, SD3 and twice-a-week thereafter (not more than 4 days apart). In the circumstances when HSCT is scheduled beyond 12 weeks from emapalumab initiation and Complete Response is maintained (see Section 5.3), the treatment with emapalumab may continue once a week; acceptable time-window for visits in this case will be ± 1 day. An EOT visit has to be performed 3 ± 1 days after last emapalumab infusion.

Furthermore, during the follow-up period, the following time-windows are allowed around visits:

- Pre-conditioning: can be combined with EOT visit provided the two visits are

not more than 2 days apart

Week (Wk) 1-2-3, D+30 post-HSCT: ±2 days
 D+60, D+100 post-HSCT: ±1 week
 6-mo, 1-yr post-HSCT: ±4 weeks

If HSCT is not performed, the described schedule applies to the follow-up visits required to occur after the last emapalumab infusion.

Following windows can be applied to the vital signs measurement:

When measured every 15 minutes: ±5 minutes
 When measured every 30 minutes: ±10 minutes

- When measured at 1 hour and 2 hours after infusion: \pm 15 minutes

Some procedures are not to be done systematically but only if clinically relevant. For example:

- ECG is mandatory at Screening and at EOT visits, however it should be done at any other timepoint during the study, if deemed appropriate.
- Brain magnetic resonance imaging (MRI) is mandatory at Screening only in case of CNS disease, but should be done at any other time-points during the study to monitor evolution or to confirm onset of CNS involvement, as clinically indicated.

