- Lumbar puncture for CSF analysis is to be performed at Screening providing that coagulation function allows, but should be done at any other time-points during the study to monitor evolution (if the initial analysis was abnormal), or to confirm new onset of CNS involvement.

- Search for pathogens (other than TB) at Screening and during the study should be done if there is any suspicion of infection, and should be performed at relevant time intervals to follow the evolution of infections, either pre-existing or emerging during the study.
- Chest X-ray should be performed at Screening and during the study in case of clinical suspicion of a pulmonary infection or to follow-up a pre-existing infection at Screening/baseline.

If planned as standard of care, alternative imaging methods will be accepted as a replacement for per protocol imaging (with exception of abdominal ultrasound): namely, brain computerized tomography (CT) or cranial ultrasound will be accepted as a replacement of brain MRI, and chest CT will be accepted as a replacement of chest X-Ray.

If CBC, coagulation, biochemistry and imaging assessments cannot be performed on the day of the scheduled visit, assessments within ± 1 day window from scheduled visit date will be accepted as a replacement.

Analysis done on blood samples will favor as much as possible the use of micro-sampling techniques.

When blood drawing needs to be limited, laboratory safety parameters (which would have been done as normal disease monitoring) will be prioritized.

Volumes of blood are calculated assuming a maximum 2-week screening, 6-month treatment period with infusions twice a week, 1-year follow-up with emapalumab detectable at all timepoints, pregnancy test performed (total study duration of 18.5 months), and amount to 98 mL for study-specific assessments (PK, PD, ADA); 253 mL for CBC, biochemistry, coagulation and pregnancy test; 31.5 mL for search for infections. Amount of blood drawn per 8 weeks of study (41.4 mL) is therefore within acceptable total blood volume draw for patients of the first year of life, and under 5% of total blood volume for older children.

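### Section 8 makes the Screening search for non-TB pathogens depend on suspicion of infection, in conflict with Table 1, Section 8.1 and footnote v

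*Protocol*

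**What the plan says.** Section 8 of the Protocol has a list introduced by "Some procedures are not to be done systematically but only if clinically relevant". One bullet in it reads "Search for pathogens (other than TB) at Screening and during the study should be done if there is any suspicion of infection". The condition covers both Screening and the later visits.

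Four other places deal with the same samples:

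- **Table 1, Search for Infections.** The general infection-search row is marked at Screening, with EBV and CMV viral loads as the minimum. The row "Atypical mycobacteria, Histoplasma capsulatum, Shigella, Salmonella, Campylobacter, Leishmania" is also marked at Screening. In both rows, suspicion of infection appears only in the columns for later visits.
- **Section 8.1.** The Screening list is introduced as mandatory. It repeats the EBV/CMV minimum. It says that the infection search follows the child's presentation, and it qualifies the exclusionary pathogens with *as appropriate*.
- **Section 8.1, footnotes v and vi.** Footnote v lets a child whose clinical assessment does not suggest these infections be enrolled before results are back, on condition that a usable specimen has been taken and is being analysed. Footnote vi limits active Leishmania screening in North America to children with recent stay in an endemic region.
- **Section 3.2.** Infection-screening samples are to be collected before the first dose, in line with the protocol's requirements. For urgent cases without suggestive findings, the section waives only the wait for results.

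The Section 8 list also says "Chest X-ray should be performed at Screening and during the study in case of clinical suspicion of a pulmonary infection", or to follow up an infection already present.

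**The concern.** The rules meet on the same child: one with active HLH, no clinical suspicion of a non-TB infection, and a need to start quickly. Footnote v and Section 3.2 let that child be dosed with results pending. The Section 8 bullet says the same child need not be sampled for anything but TB. If a site follows the bullet, there may be no result to wait for.

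Two things are at stake. The first is eligibility. Sites that follow Table 1 and sites that follow Section 8 would apply the non-TB part of exclusion criterion 2 on different evidence, before giving a drug that neutralises IFNγ. Section 9.4.2.2 names mycobacteria, Salmonella and Histoplasma as risks when IFNγ activity is lost. It also reports a disseminated histoplasmosis in NI-0501-04 that ended treatment. For the enteric pathogens, Sections 1.2.2.2 and 9.4.2.2 tie infection in monkeys to organisms already in the gut before dosing.

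The second is the safety baseline. EBV and CMV are not exclusionary, but Section 9.1 follows viral load whether present at baseline or emerging later. Without a Screening value that distinction is harder to make.

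**Working it through.** No arithmetic beyond a count applies, so the check sets the texts side by side.

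**Step 1. Apply each rule to a child with no suspicion of infection at Screening.**

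| Source | EBV/CMV viral loads | Exclusionary non-TB pathogens |
|---|---|---|
| Section 8 bullet | Not required | Not required |
| Table 1, Screening column | Required (stated minimum) | Required (row marked) |
| Section 8.1 | Required (stated minimum) | Listed, but *as appropriate* |
| Footnote v | Not addressed separately | A usable specimen is a condition of starting before results |
| Section 3.2 | Samples before first dose, by reference to other requirements | Same |

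For EBV/CMV, Section 8 contradicts two explicit statements, and nothing qualifies them. For the exclusionary pathogens, Section 8 contradicts Table 1 and does not fit footnote v, whose subject is exactly the child without suggestive findings. Section 3.2 adds only an indirect conflict. It defers to requirements set elsewhere, but its waiver presupposes that a sample exists.

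**Step 2. See whether Table 1 leaves Screening conditions unstated.** It does not. Brain MRI carries a footnote, "to be performed in case of CNS disease and/or onset of neurological signs and/or symptoms", and CSF analysis carries a coagulation proviso. The pathogen row carries no condition at Screening.

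**Step 3. Compare all five bullets in the Section 8 list with the Table 1 Screening column.**

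| Section 8 bullet | Table 1 at Screening | Result |
|---|---|---|
| "ECG is mandatory at Screening and at EOT visits" | Marked | Match |
| Brain MRI, only with CNS disease | Marked, same condition by footnote | Match |
| "Lumbar puncture for CSF analysis is to be performed at Screening providing that coagulation function allows" | Marked, if coagulation allows | Match |
| Non-TB pathogen search, if suspicion | Marked; suspicion only later | Conflict |
| Chest X-ray | Marked; condition only later | Ambiguous |

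Tally: 3 match + 1 conflict + 1 ambiguous = 5.

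**Step 4. Read the chest X-ray bullet.** Its condition can attach to both time points or only to the later one. On the second reading it means at Screening, and afterwards if suspected. That agrees with Table 1, where the text "If clinically indicated (e.g. in case of clinical suspicion of pulmonary infection" belongs to the visits after Screening. Section 8.1 lists the X-ray without a condition, and footnote v treats it as part of the clinical assessment. Section 3.2 does not mention it.

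**The case against.** The best defence is that the documents largely settle which text governs. Section 8 is an outline. Before the list it sends the reader to Table 1 for the detailed schedule, and it offers the bullets as examples. Section 8.1 is the specific Screening section and calls its procedures mandatory. This lowers the chance that a site is misled. But no sentence gives Table 1 precedence, and the bullet is a specific instruction that names Screening.

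A second defence is intent. Section 8.1 uses *as appropriate* and refers to the child's presentation, and the summary of changes for version 4.0 says infection search was made more flexible while remaining rigorous. This has force for the exclusionary pathogens. Footnote v also sits under a heading that includes TB and asks for a usable specimen, not one per organism. A reader might infer from Table 1 that five of the six listed organisms or groups must be tested in every child, with only Leishmania excepted. Section 8.1 does not support that reading. None of this touches the EBV/CMV minimum, which version 4.0 keeps in both places.

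A third defence is that the practical risk is thin. Any suspicion is a low threshold in children with active HLH, in whom fever is a diagnostic criterion. Appendix C asks, in joint review with the sponsor, whether each of these infections has been excluded. Exclusion criterion 2 concerns active infection, whereas the toxicology concerns carriage and covers three of the six organisms or groups. These points stand and limit the size of the problem. They do not remove it: Appendix C accepts an affirmative answer without asking whether a specimen was taken.

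**Conclusion.** The pathogen bullet in Section 8 is wrong as written. It conflicts directly with Table 1 and with the EBV/CMV minimum in Section 8.1, does not fit footnote v, and conflicts only indirectly with Section 3.2. The conflict is firm for EBV/CMV. For the exclusionary pathogens it is real but softened by Section 8.1 and, for Leishmania in North America, by footnote vi.

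A reader might infer that the chest X-ray bullet is a second contradiction. The documents do not support that: its wording has a natural reading that agrees with Table 1. It is an ambiguity worth removing.

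A reader might also infer that children will be dosed unscreened in appreciable numbers. The documents give no basis for a figure. The number may be small, and TB testing is unaffected. The conclusion assumes that Table 1 and footnote v express the intended Screening rule; if they do not, the same inconsistency has to be resolved in the other direction.

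**What to change.** 1. In the Section 8 pathogen bullet, limit the suspicion condition to visits after Screening.
2. Add that at Screening the EBV and CMV viral loads and the specimens for the exclusionary pathogens (Leishmania as in footnote vi) are taken before the first dose, per Table 1 and Section 8.1, and that results may be pending.
3. Reword the chest X-ray bullet to: at Screening; thereafter in case of clinical suspicion or to follow a pre-existing infection.
4. If suspicion-only testing was intended for the exclusionary pathogens, amend Table 1 and footnote v instead.

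Under items 1 to 3 the cost is two reworded bullets and one added sentence; no procedure is added beyond Table 1. The downside is that sites which relied on the Section 8 bullet would have to sample children without suspicion, as Table 1 already asks. Naming accepted specimen types in Section 8.1 and copying footnote vi into Table 1 would help sites but are optional.

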8.1 SCREENING

Patients will be screened for eligibility prior to enrolment into the study. An Eligibility Review Form (Appendix C) will be completed and shared with the Sponsor after the patient is consented, to guide the joint review of patient's eligibility.

A pre-screening checklist (Appendix D) is an additional tool to assist the Investigator to make decisions such as patient transfer,. This checklist enables rapid preliminary assessment of patient's eligibility based strictly on the information available from routine patient care. The pre-screening checklist does not need to be shared with the Sponsor

A screening log will be maintained by the Investigator with specification of reasons for non-eligibility.

Screening evaluations should be completed within the 2 weeks prior to the first administration of study drug (Visit 1). Evaluations performed before ICF signature, but within this window and as per routine care, will be accepted for screening purposes. Patient's medical record should clearly denote these evaluations as standard of care.

The following information must be collected and the following procedures must be performed:

Protocol NI-0501-09 Version 4.0 Global – Final 31 March 2020

CONFIDENTIAL

^{iv} WHO | Blood Sample Volumes in Child Health Research: Review of Safe Limits." n.d. WHO. https://doi.org//entity/bulletin/volumes/89/1/10-080010/en/index.html.

Patient information:

- Demographic and medical history, including race, ethnicity and country of origin, if allowed per local Regulations
- Medications at Screening
- Any conventional HLH therapy previously received
- Date of HLH diagnosis and HLH history
- Molecular diagnosis of HLH, as available
- Perforin expression and other functional tests performed for the diagnosis of HLH, as available
- Date and criteria of eligibility

Clinical Assessment:

- Vital signs, including body temperature, heart rate, blood pressure, and oxygen saturation
- Physical examination, including at a minimum, weight, height/length, spleen and liver size (by abdominal palpation), and neurological examination
- Quality of Life questionnaire: PedsQL[™], Pediatric Quality of Life Inventory[™]

Procedure:

ECG

Search for infections^v:

- Tuberculosis mycobacteria via interferon-gamma release assays (IGRA)/ purified protein derivative (PPD) test and polymerase chain reaction (PCR). In a patient having received BCG vaccination, a PPD test must be performed and combined with IFNγ-release assay if the PPD result is ≥5 mm. In addition, search for Tuberculosis via PCR in any relevant specimen should be performed to have a baseline, as this test will be used during the course of the study to perform regular TB monitoring.
- Infection search at Screening should be performed according to the patient's clinical presentation. At a minimum EBV and CMV viral loads should be assessed.
- Atypical mycobacteria, Histoplasma capsulatum, Shigella, Salmonella, Campylobacter and Leishmania^{vi}, as appropriate. The presence of Leishmania can also be ascertained by direct bone marrow observation. A first screening for Histoplasma capsulatum may be performed using galactomannan assay, however -if the test

^v A patient with a clinical assessment (including chest X-ray) not indicative of the presence of the above mentioned infections, provided that a usable specimen has been taken, and the microbiological analysis is ongoing, can be enrolled prior to the availability of the results, if a patient's medical condition warrants rapid treatment initiation.

vi As *Leishmania* is not endemic in North America, only patients who have been in endemic regions (e.g., South America) during the 6 months prior to Screening, are required to be actively screened for *Leishmania*.

Study NI-0501-09 NI-0501 in Primary HLH Page 50 of 92

is positive- confirmation should be obtained by using a *Histoplasma* capsulatum specific test.

Laboratory:

- CBC with differential count (including large unstained cells count, whenever performed as routine)
- Coagulation tests: activated partial thromboplastin time and/or ratio, prothrombin time and/or International Normalized Ratio (INR), Ddimers and fibrinogen
- Biochemistry: glucose, ferritin, C-reactive protein (CRP), liver function (aspartate amino transferase [AST], ALT, gamma glutamy transferase [γGT], lactate dehydrogenase [LDH], alkaline phosphatase [ALP], bilirubin), renal function (albumin, creatinine and urea) and triglycerides (fasting whenever possible)
- Pregnancy test (blood or urine), if applicable

Imaging:

- Abdominal ultrasound (spleen longitudinal measure)
- Chest X-ray (or chest CT as an alternative)
- Brain MRI to be performed in case of CNS disease (brain CT or cranial ultrasound as an alternative)

Histopathology:

CSF Analysis (if coagulation allows)

Safety:

Recording of any AEs occurred since signature of the ICF

